### **3.9.3 Vital Signs**

Descriptive statistics for vital signs (weight, temperature, blood pressure, pulse rate, and respiratory rate) values and the change from baseline will be presented for each scheduled assessment time point.

### **3.9.4 ECG**

Descriptive statistics for ECG parameters (i.e., PR interval, QRS interval, and QTcF interval) at each time point with triplicate ECGs will be presented for the values and change from baseline scores. (QTcF is the QT interval using Fridericia's correction which is calculated by  $QTcF = QT/RR^{1/3}$ .)

The number and percentage of subjects with observed QTcF values that satisfy the following conditions will be presented by treatment group and study visit and categorized as:  $\leq 450$  ms;  $> 450$  to  $480$  ms;  $> 480$  to  $500$  ms; and  $> 500$  ms.

The number and percentage of subjects having change from baseline QTcF values that satisfy the following conditions will be presented by treatment group and study visit and categorized as:  $\leq 0$  ms;  $> 0$  to  $\leq 30$  ms;  $> 30$  to  $\leq 60$  ms; and  $> 60$  ms.

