Methodology	
Subjects who have signed an Institutional Review Board (IRB)/Independent Ethics Committee- (IEC)-approved informed consent form (ICF) and who have met all of the inclusion/exclusion criteria will be enrolled.
 
Approximately 48 subjects will be enrolled to receive orally administered KD025 200 mg once daily (QD), KD025 200 mg twice daily (BID), or KD025 400 mg QD. Study drug will be administered in 28-day cycles until disease progression or unacceptable toxicity occurs. Subjects may receive study drug in the inpatient or outpatient setting.
 
 
 Cohort 1	16 subjects	200 mg KD025 QD	
 
 Cohort 2	16 subjects	200 mg KD025 BID	
 
 Cohort 3	16 subjects	400 mg KD025 QD	
 
 
BID = twice daily; QD = once daily
 
Prior to enrolling subsequent cohorts, the safety data in each previous cohort will be evaluated after 8 subjects have reached 2 months of treatment to assure there is no safety signal. If $\geq 25\%$ of subjects in a cohort experience a Common Terminology Criteria for Adverse Events (CTCAE) v4.03 Grade 2 liver toxicity or a CTCAE v4.03 Grade 3 (or higher) adverse event (AE) in the same organ or body system, or if $> 25\%$ of subjects in a cohort are discontinued for toxicity that persists for 14 days, then dose escalation to the next cohort will not occur, and all subjects in that dose cohort will be dose reduced.
 
If $\geq 25\%$ of subjects in the 200 mg QD cohort experience a CTCAE v4.03 Grade 2 liver toxicity or a CTCAE v4.03 Grade 3 (or higher) AE in the same organ or body system, or if $> 25\%$ of subjects in a cohort are discontinued for toxicity that persists for 14 days, then further dosing will not occur and the study will be terminated.
 
Response criteria will be assessed on Day 1 of each cycle, starting at Cycle 2 Day 1, as well as the end of treatment (EOT) visit using the criteria of 2014 NIH Consensus Development Project on Clinical Trials in cGVHD (CR, PR, or lack of response (unchanged, mixed, or progression)); see Appendix B).
 
cGVHD severity (clinician-reported) and symptom (subject-reported) assessments will be performed on Day 1 of each cycle starting at Cycle 1 Day 1 as well as the EOT visit using the Physician-reported Global Chronic GVHD Activity Assessment form (Appendix A), cGVHD Activity Assessment: Patient Self Report, and Lee cGVHD Symptom Scale (see Appendices C and D).
 
At Cycle 25 Day 1 (C25D1) and all odd cycles thereafter (ie, C27D1, C29D1, C31D1, etc.), subjects will receive 2 cycles worth of study drug along with 2 diaries and will return to the clinic at the next odd cycle for
	Cohort 1	16 subjects	200 mg KD025 QD	Cohort 2	16 subjects	200 mg KD025 BID	Cohort 3	16 subjects	400 mg KD025 QD

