8.4.3 Cycles 2 and Beyond, Day 1 (± 3 days)

On Day 1 of Cycles 2 and beyond, subjects will come to the clinic to have the following procedures completed:

- Complete PE, including weight
- Seated vital sign measurements (sitting blood pressure, pulse, respiratory rate, temperature)
- Karnofsky Performance Scale score
- Clinical laboratory tests (hematology and serum chemistry panel)
- TSH
- Urinalysis
- Supine 12-Lead ECG; pre-dose on Day 1 of Cycle 4 and Cycle 7 only; to be performed 3 times consecutively within 30 minutes (must have an interval of at least 1–2 minutes between ECGs)
- Urine pregnancy test (for women of childbearing potential. Positive results are to be confirmed with serum testing.)

- Pulmonary function tests (including FEV₁, FVC, DL_{CO}, TLC, and RV; to be performed every other cycle, starting with Cycle 3 for subjects without lung involvement)
- PK sample collection (Cycle 2 only at the following time points: pre-dose [Time 0], and 1, 2, 3, 4, 5, and 6 hours after dosing [after first dose for subjects in the BID group]); a pre-dose sample is to be collected at the Cycle 4 and Cycle 7 visit
- PD blood sample collection (Cycles 2, 4, and 7 only: pre-dose)
- Study drug administration
- Dispense/Collect study drug
- Collect study drug diary
- Response assessment.
- Physician-Reported Global cGVHD Activity Assessment
- cGVHD Activity Assessment - Patient Self Report
- Lee cGVHD Symptom Scale
- Concomitant medications assessment
- AE assessment

At Cycle 25, Day 1 (C25D1), and all odd cycles thereafter (i.e., C27D1, C29D1, C31D1, etc.), subjects will receive 2 cycles worth of study drug along with 2 diaries and will return to the clinic at the next odd cycle for assessments and IP accountability. Investigators and/or subjects have the option of coming into clinic at one or more even cycles (i.e., C26D1, C28D1, C30D1, etc). On even cycles, when patients do not come to clinic, the study staff will contact the patient via phone and document any new adverse events and concomitant medications.

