8.7. Unscheduled Visits

For subjects requiring an unscheduled visit, the following assessments may be performed at the investigator's discretion:

- Complete PE, including weight
- Seated vital sign measurements (sitting blood pressure, pulse, respiratory rate, temperature)
- Karnofsky Performance Scale score
- Clinical laboratory tests (hematology and serum chemistry panel)
- TSH
- Urinalysis
- Supine 12-Lead ECG; to be performed 3 times consecutively within 30 minutes (must have an interval of at least 1–2 minutes between ECGs); perform ECG immediately prior to blood sample collection, if possible
- Urine pregnancy test (for women of childbearing potential. Positive results are to be confirmed with serum testing.)
- Pulmonary function tests (including FEV₁, FVC, DL_{CO}, TLC, and RV)
- Collect study drug (if appropriate)
- Collect study drug diary (if appropriate)
- Physician-Reported Global cGVHD Activity Assessment
- cGVHD Activity Assessment - Patient Self Report
- Lee cGVHD Symptom Scale
- Concomitant medications assessment
- AE assessment

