9.3. Electrocardiogram Assessments

A digital 12-lead ECG will be obtained during the study (see [Table 1](#) for timing of ECG assessments and [Table 2](#) for timing allowances).

Digital 12-lead ECG recordings are to be made with the subject in a supine position having rested in this position for at least 5 minutes before each reading. ECGs are to be performed 3 times consecutively within 30 minutes (must have an interval of at least 1–2 minutes between ECGs). At each visit, the ECG is to be performed immediately before any blood sample collection, if possible.

The following ECG parameters will be collected: PR interval, QRS interval, and QTc[F]. The ECG findings will be evaluated by a qualified physician for the presence of abnormalities (qualitative assessment). The physician will assess each ECG as normal, abnormal/not clinically significant, or abnormal/clinically significant.

Abnormalities in the ECG that lead to a change in subject management (eg, dose reduction or delay, requirement for additional medication or monitoring) or result in clinical signs and symptoms are considered clinically significant for the purposes of this study and will be recorded in the AE eCRF. If ECG abnormalities meet criteria defining them as serious, they must be reported as an SAE (see [Section 16.3.1](#)).

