### **3.9 Safety Analysis**

Safety assessments will include AEs, serious adverse events (SAEs), vital sign measurements, clinical laboratory evaluations (hematology and chemistry), and electrocardiograms (ECGs). Unscheduled visits for safety assessments will not be presented in summary tables but will be in listings. All safety analyses will be performed using the safety population.

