F	Liver function test: Distribution of ALT over time by cohort	Safety
F	Liver function test: Mean AST over time by cohort	Safety
F	Liver function test: Mean change from baseline of AST over time by cohort	Safety
F	Liver function test: Distribution of AST over time by cohort	Safety
F	Liver function test: Mean alkaline phosphatase over time by cohort	Safety
F	Liver function test: Mean change from baseline of alkaline phosphatase over time by cohort	Safety
F	Liver function test: Distribution of alkaline phosphatase over time by cohort	Safety
F	Liver function test: Mean total bilirubin over time by cohort	Safety
F	Liver function test: Mean change from baseline of total bilirubin over time by cohort	Safety
F	Liver function test: Distribution of total bilirubin over time by cohort	Safety
T	Vital signs shift table of vital signs by visit and cohort	Safety
T	Change from baseline of in ECG by visit and cohort	Safety
T	Number and percentage of subjects with QTcF by visit and cohort	Safety
T	Number and percentage of subjects with QTcF change from baseline by visit and cohort	Safety
L	Deaths during on-treatment period by cohort	Safety
L	Adverse events by cohort	Safety

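### QTcF categories are tabulated only by visit, with unscheduled ECGs left out, so no planned summary counts the subjects per cohort who ever crossed a QTcF threshold on treatment

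*SAP*

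**What the plan says.** SAP 3.9.4 sets four categories for observed QTcF (up to 450, above 450 to 480, above 480 to 500, and above 500 ms) and four for change from baseline (up to 0, above 0 to 30, above 30 to 60, and above 60 ms). For the first set: "The number and percentage of subjects with observed QTcF values that satisfy the following conditions will be presented by treatment group and study visit". The second set is presented in the same way. SAP Table 6 lists the matching outputs as "Number and percentage of subjects with QTcF by visit and cohort" and "Number and percentage of subjects with QTcF change from baseline by visit and cohort". The only other ECG table there, change from baseline in ECG parameters, is also by visit and cohort.

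SAP 3.9 adds a general rule: "Unscheduled visits for safety assessments will not be presented in summary tables but will be in listings".

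The protocol synopsis plans descriptive ECG statistics at each scheduled time point, plus listings. Scheduled on-treatment ECGs are at Cycle 1 Day 1 (4 hours after the dose) and then "Supine 12-Lead ECG; pre-dose on Day 1 of Cycle 4 and Cycle 7 only" (Protocol 8.4.3; Table 1, footnote d). The next scheduled ECG is at the 28-Day Follow-Up, after dosing has ended. ECGs can also be taken at unscheduled visits, at the investigator's discretion: "Supine 12-Lead ECG; to be performed 3 times consecutively within 30 minutes" (Protocol 8.7). Footnote d allows one to be requested when a subject stops treatment early, but the EOT list in Protocol 8.5 contains no ECG.

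**The concern.** The SAP chose thresholds whose natural use is at subject level: how many subjects in each dose cohort reached 480 or 500 ms, or rose by more than 60 ms, while on drug. No planned table answers that. A by-visit row counts subjects at one visit. Rows cannot be added, because the same subject may appear in several, and ECGs taken off schedule appear in none.

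Safety and tolerability is a primary objective. The protocol excludes QTcF above 450 ms at entry (Protocol 7.3) and asks for caution with QT-prolonging drugs (Protocol 15). The adverse event tables do not close the gap. Protocol 9.3 treats as clinically significant "Abnormalities in the ECG that lead to a change in subject management (eg, dose reduction or delay, requirement for additional medication or monitoring"), and also those that produce signs or symptoms; these are recorded as adverse events. An exceedance that does neither need not appear there. Laboratory data do get a subject-level worst on-treatment grade (SAP 3.9.2 and Table 6); QTcF has no counterpart.

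**Working it through.** The plan states no figure on this point, so there is none to reproduce. The check has three parts.

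**1. Is there a subject-level QTcF summary anywhere?** SAP 3.9.4 is by visit. The three ECG entries in SAP Table 6 are by visit and cohort. The protocol synopsis is by scheduled time point. SAP 3.9 removes unscheduled visits from all safety summary tables. Neither document plans a maximum, worst or ever-on-treatment QTcF count.

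**2. What do by-visit counts say about the ever-exceeded count?** Let c1, c2, c3 be the numbers above a threshold at the three scheduled on-treatment ECGs, and E the number of subjects above it at one or more of them. Then

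max(c1, c2, c3) ≤ E ≤ min(n, c1 + c2 + c3).

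Take n = 16 per cohort (SAP 3.12). The counts below are assumed, and all 16 subjects are taken to have an ECG at each time.

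| By-visit counts | E at least | E at most |
|---|---|---|
| one at each of two visits | 1/16 = 6.3% | 2/16 = 12.5% |
| 1, 1, 1 | 1/16 = 6.3% | 3/16 = 18.8% |
| 2, 2, 2 | 2/16 = 12.5% | 6/16 = 37.5% |

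If every row is zero, or only one visit has exceedances, the two bounds coincide and the rows do give the scheduled ever-count.

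The same point in terms of rates: for an assumed per-visit rate p, the ever-rate over three visits is p if the same subjects exceed each time, and 1 − (1 − p)³ if visits are independent. For p = 2%, 5% and 10% the independent values are 5.9%, 14.3% and 27.1%.

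For one subject whose only exceedance is on an unscheduled ECG, every row shows 0/16, while the true ever-count is 1/16 = 6.3%.

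**3. How much treatment time has no scheduled ECG?** With 28-day cycles, the nominal days are:

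- Cycle 1 Day 1: Day 1
- Cycle 4 Day 1: 3 × 28 + 1 = Day 85
- Cycle 7 Day 1: 6 × 28 + 1 = Day 169
- Cycle 25 Day 1: 24 × 28 + 1 = Day 673

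The protocol synopsis provides for treatment this long and beyond ("At Cycle 25 Day 1 (C25D1) and all odd cycles thereafter"). A subject who reaches Cycle 25 Day 1 is 673 − 169 = 504 days, or 504 / 28 = 18 cycles, past the last scheduled on-treatment ECG. A QTcF rise in that period could be recorded only on an unscheduled or early-discontinuation ECG. The first kind is barred from the tables, and the second has no row named for it.

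**The case against.** The strongest reply is that this asks for an optional display in an exploratory Phase 2a study. The SAP meets the protocol's commitment to summaries by scheduled time point and goes further by adding categories. That stands: this is a missing summary, not a conflict between protocol and SAP.

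By-visit descriptive statistics include the maximum (SAP 3.1.2), so each cohort's highest scheduled QTcF and largest scheduled rise will be visible. This also stands for scheduled ECGs. It shows that a high value occurred, but not in how many subjects, and it shows nothing taken off schedule.

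Adverse event capture is broad, since a need for extra monitoring is enough to make an ECG abnormality an adverse event. That leaves a narrow case: an off-schedule exceedance that prompts no action and causes no symptoms. Such a value would still be in the listings the plan promises, although Table 6 names no ECG listing, and with about 48 subjects a hand count is feasible.

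The 504-day gap is a choice of schedule, and a new row creates no ECGs. That is right; it matters only because any on-treatment ECG in that period would be off schedule. Similarly, the early-discontinuation ECG is not expressly excluded from the tables, but nothing says where it goes.

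The laboratory contrast has an innocent explanation, because the known safety signal is hepatic. Finally, ECGs done for cause can push up an ever-rate. That is a real drawback, and keeping the by-visit rows beside the new one makes it visible.

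**Conclusion.** The concern holds, as a minor point that is cheap to correct. As written, the plan gives no count per cohort of subjects who ever crossed a QTcF threshold on treatment. When exceedances fall at two or more visits the tables leave that count undetermined, and a subject whose only exceedance was at an unscheduled visit is shown as zero throughout.

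The size depends on events the documents do not predict. With 16 per cohort and assumed counts of one per visit, the uncertainty is 1 to 3 subjects. If there are no exceedances on or off schedule, nothing is lost. No QT signal is reported, and no dose-escalation or stopping rule depends on these tables. No data are missing; what is missing is the summary.

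**What to change.** In SAP 3.9.4 and in both QTcF tables of SAP Table 6, add a row for the maximum on-treatment post-baseline value, by cohort and overall.

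- **Content:** classify each subject once by the highest QTcF and once by the largest increase from baseline.
- **Window:** all ECGs after the first dose up to the EOT visit, which Protocol 8.5 places within 3 days of the last dose. Include unscheduled and early-discontinuation ECGs.
- **Value used:** the mean of the triplicate at each ECG time, since SAP 3.9.4 does not say how the readings are combined.
- **Denominator:** subjects with at least one such ECG and, for change, a baseline.
- **Other rows:** keep the by-visit rows, and show the 28-Day Follow-Up ECG separately.
- **SAP 3.9:** add an exception for this row to the rule on unscheduled visits.

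The cost is one row in each of two existing tables, a little programming and one sentence in SAP 3.9. No new data are collected. For-cause ECGs may raise the reported rate slightly; a footnote should say that the row includes them.

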### **3.10 Pharmacokinetic Analysis**

Further details will be described in the Pharmacokinetic Analysis Plan.

### **3.11 Pharmacodynamic Analysis**

Further details will be described in the Pharmacodynamics Analysis Plan.

### **3.12 Sample Size Justification**

The total sample size of 16 subjects per KD025 dose group will provide  $> 90\%$  probability of  $\geq 1$  subject experiencing an AE that has an underlying rate of  $\geq 14\%$  and  $> 80\%$  probability of  $\geq 1$  subject in the study experiencing an AE that has an underlying rate of  $\geq 10\%$ .

### **3.13 Interim Analysis**

This is a dose-escalation, open-label study. Interim analyses may occur periodically during the course of this trial. There is no early stopping for efficacy.

### **3.14 Primary CSR Analysis**

A primary CSR analysis will be conducted 1 year after the last subject is enrolled.

## 4 LIST OF TABLES, FIGURES, AND LISTINGS

In all tables, figures and listing, results will be presented by treatment cohorts and overall, unless be otherwise specified.

[Table 3](#) lists demographic and baseline characteristics TLFs; [Table 4](#) lists treatment exposure and concomitant medication TLFs; [Table 5](#) lists efficacy TLFs; and [Table 6](#) lists safety TLFs.

**Table 3. Demographics and Baseline Characteristics TLFs**

T/F/L	Title	Population
T	Analysis populations by cohort (mITT Population)	mITT
T	Subject disposition	mITT
L	Subject disposition	mITT
T	Summary of follow-up duration	mITT
L	Protocol deviations	mITT
T	Demographics and baseline characteristics	mITT
L	Demographics and baseline characteristics	mITT
T	Medical histories by primary system organ class and preferred terms	mITT
L	Medical history	mITT
T	cGVHD and transplant history	mITT
L	cGVHD and transplant history	mITT
T	Summary of organ involvement at baseline and baseline score	mITT
T	Summary of prior systemic cGVHD therapy	mITT
T	Summary of prior systemic cGVHD therapy by ATC class	
L	Prior systemic cGVHD therapy	mITT

**Table 4. Treatment Exposure and Concomitant Medication TLFs**

T/F/L	Title	Population
T	Concomitant corticosteroid medications for cGVHD by ATC class, preferred term and cohort	mITT
L	Concomitant corticosteroid medications for cGVHD by cohort and subject	mITT
T	Concomitant calcineurin inhibitors for cGVHD by ATC class, preferred term and cohort	mITT
L	Concomitant calcineurin inhibitors for cGVHD by cohort and subject	mITT
T	Concomitant medications prior to the start of study drug by ATC class, preferred term and cohort	mITT
L	Concomitant medications prior to the start of study drug by cohort and subject	mITT
T	Concomitant medications after the start of study drug by ATC class, preferred term and cohort	mITT
L	Concomitant medications after the start of study drug by cohort and subject	mITT
T	KD025 treatment exposure and compliance	mITT
T	KD025 dose reductions and interruptions	mITT
L	KD025 dose reductions and interruptions	mITT

**Table 5. Efficacy TLFs**

T/F/L	Title	Population
Primary Endpoint: ORR		
T	Overall Response Rate	mITT
T	Best Overall Response	mITT
L	Listing of Overall Response by subject by visit	mITT
Secondary Endpoint: DOR		
T	Descriptive Kaplan-Meier and landmark statistics for primary DOR	Responder
F	Kaplan-Meier plot of primary DOR	Responder
L	Listing of all primary DOR episodes for each subject	Responder
T	Descriptive Kaplan-Meier and landmark statistics for secondary DOR	Responder
F	Kaplan-Meier plot of secondary DOR	Responder
L	Listing of all secondary DOR episodes for each subject	Responder
T	Descriptive Kaplan-Meier and landmark statistics for tertiary DOR	Responder
F	Kaplan-Meier plot of tertiary DOR	Responder
L	Listing of all tertiary DOR episodes for each subject	Responder
T	Descriptive Kaplan-Meier and landmark statistics for quaternary DOR	Responder
F	Kaplan-Meier plot of quaternary DOR	Responder
L	Listing of all quaternary DOR episodes for each subject	Responder
Secondary Endpoint: TTR		
T	Descriptive statistics for time to response (TTR) and cumulative response rate over time	Responder
L	Listing of TTR for each subject	Responder
Secondary Endpoint: Response by Organ System		
T	Best response by individual organ	mITT
T	Best response by individual organ	Responder
L	Listing of organ score and response assessment by subject and visit	mITT
T	Descriptive statistics for time to response (TTR) and cumulative response rate over time by organ	mITT
T	Descriptive statistics for time to response (TTR) and cumulative response rate over time by organ	Responder
Secondary Endpoint: TTNT		
T	Descriptive Kaplan-Meier and landmark statistics for TTNT	mITT
F	Kaplan-Meier plot for TTNT	mITT
Secondary Endpoint: Corticosteroid Dose		
T	Descriptive statistics for prednisone equivalent dose of corticosteroids	mITT Responder

T/F/L	Title	Population
		Non-responder BL corticosteroid dose level (upper and lower 50 th percentiles)
T	Summary of raw and change from baseline on prednisone equivalent dose of corticosteroids by visit	mITT Responder Non-responder BL corticosteroid dose level (upper and lower 50 th percentiles)
L	Listing of all the steroid raw and standardized dosing by subject and visit	mITT
Secondary Endpoint: CNI Dose		
T	Summary of descriptive statistics for CNI	mITT
L	Listing of all the CNI dosing by subject and visit	mITT
Secondary Endpoint: FFS		
T	Descriptive Kaplan-Meier and landmark statistics for FFS (with cumulative failure rates for each of the 3 components FFS)	mITT
F	Kaplan-Meier plot for FFS (with cumulative failure rates for 3 components of failures)	mITT
L	Listing of failure events	mITT
Secondary Endpoint: Change in cGVHD severity as based on the Clinician-reported Global cGVHD Activity Assessment		
T	Maximal change from baseline in global severity rating based on Clinician-reported cGVHD Assessment	mITT
Secondary Endpoint: Symptom activity using the cGVHD Activity Assessment Patient Self-Report		
T	Maximal change from baseline in symptom activity (scored 0-10) based on cGVHD Activity Assessment Patient Self Report	mITT
T	Summary of severity rating on categorical status (none, mild, moderate, severe) based on cGVHD Activity Assessment Patient Self Report by visit	mITT
T	Descriptive statistics of cGVHD symptoms based on cGVHD Activity Assessment Patient Self Report (change of cGVHD symptom to a month ago) by visit	mITT
Secondary Endpoint: LSS score		

T/F/L	Title	Population
T	Descriptive statistics for LSS score	mITT Responder Non-responder
T	Summary of LSS Score (overall and each of seven domains) raw and change from baseline by visit	mITT Responder Non-responder
L	Listing of Lee Symptom Scale Score by subject, domain and visit	mITT
Subgroup analyses (subgroups are listed in section 3.8.4 Subgroup Analyses )		
T	Overall Response Rate by Subgroup	mITT
T	Descriptive Kaplan-Meier and landmark statistics for primary DOR by subgroup	mITT
F	Kaplan-Meier plot of all DOR by subgroup	mITT
L	Listing of PPI patients by cohort	mITT

